1.27.2 UNANTICIPATED PROBLEM REPORTING

The investigator will report unanticipated problems (UPs) to the reviewing Institutional Review Board (IRB) and to the Data Coordinating Center (DCC)/lead principal investigator (PI). The UP report will include the following information:

- Protocol identifying information: protocol title and number, PI's name, and the IRB project number:
- A detailed description of the event, incident, experience, or outcome;
- An explanation of the basis for determining that the event, incident, experience, or outcome represents an UP;
- A description of any changes to the protocol or other corrective actions that have been taken or are proposed in response to the UP.

To satisfy the requirement for prompt reporting, UPs will be reported using the following timeline:

- UPs that are serious adverse events (SAEs) will be reported to the IRB and to the DCC/study sponsor within 5 days of the investigator becoming aware of the event.
- Any other UP will be reported to the IRB and to the DCC/study sponsor within 1 week of the investigator becoming aware of the problem.
- All UPs should be reported to appropriate institutional officials (as required by an institution's
 written reporting procedures), the supporting agency head (or designee), and the Office for
 Human Research Protections (OHRP) within 1 week of the IRB's receipt of the report of the
 problem from the investigator.

1.27.3 REPORTING UNANTICIPATED PROBLEMS TO PARTICIPANTS

N/A

STATISTICAL CONSIDERATIONS

1.28 STATISTICAL HYPOTHESES

Primary Efficacy Endpoint(s):

To determine if early treatment with NAC after head injury results in improved olfactory function, compared to placebo. Type of comparison: superiority. Time period: 1 and 3 months post-enrollment.

Null hypothesis: There is no difference in SIT score with NAC treatment or placebo. Alternative hypothesis: NAC treatment results in improved SIT score.

• Secondary Efficacy Endpoint(s):

To assess olfactory-specific quality of life measure in treated versus placebo groups. Type of comparison: superiority. Time period: 1 and 3 months post-enrollment.

Null hypothesis: There is no difference in QOD score with NAC treatment or placebo. Alternative hypothesis: NAC treatment results in improved QOD score.

1.29 SAMPLE SIZE DETERMINATION

Number of participants to enroll to have adequate power to test the key hypotheses for the study:

Placebo group: 30 Treatment group: 30

- Target study sample size: 30 subjects in each arm, 60 subjects total. Anticipated number to be screened in order to reach the target enrollment: 300 subjects (approximately 33% of trauma subjects may have abnormal SIT scores; of these, approximately 40% may have other exclusions or decline).
- Outcome measure used for calculations: SIT score
- Test statistic: t-test
- Null and alternative hypotheses:

Null hypothesis: There is no difference in SIT score with NAC treatment or placebo.

Alternative hypothesis: NAC treatment results in improved SIT score.

• Type I error rate (alpha): 0.05

Power level: 0.8

• Assumed mean and variance: Placebo group, mu1: SIT=17 ± 10

Treatment group, mu2: SIT=25 ± 10

Reference: "Hypothesis Testing: Two-Sample Inference - Estimation of Sample Size and Power for Comparing Two Means" in Rosner, Bernard Fundamentals of Biostatistics, Belmont, Calif.: Duxbury Press, [1995].

SIT score of 17 is used for the placebo group because this is at the upper range of a score categorized as anosmia (total loss of olfaction). In a recent large review and meta-analysis of TBI-induced olfactory loss¹ a range of SIT scores are reported in the 7-27 score range, for mild-moderate TBI. Based on these data, we anticipate identifying and enrolling patients with a mean score of approximately 17 and a variance of approximately 10.

In terms of estimated possible improvement in SIT score with NAC treatment, we have chosen an increase of 8 ± 10 points, because a jump of more than a few points on a repeat SIT test after one

month is considered to be greater than just random chance¹¹; (and [name], *personal communication*). There are no published data available for specifically measuring olfactory change following treatment with NAC for head trauma. In a pilot study testing topical intranasal NAC for different forms of anosmia (Clinicaltrials.gov), no published results are available. However, in a study using the same dosage regimen of oral NAC following blast TBI and assessing non-olfactory outcome measures, quantifiable neuropsychiatric measures did show a roughly 25-33% improvement versus placebo, providing an additional indirect basis for expecting a similar magnitude effect on our measures³.

- Anticipated impact of dropout rates, withdrawal, missing data, etc. on study power: to compensate for such issues, we have increased our sample size by 5 subjects per group.
- Secondary endpoint: We have included a secondary endpoint to measure quality of life via a
 validated questionnaire (QOD). We have no specific guides for mean or variance for the
 questionnaire in terms of possible NAC or placebo treatment, so no calculations are possible.
 Nonetheless, a simple questionnaire poses no cost or risk, such that we see no reason to not
 collect these data.

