1.23 LOST TO FOLLOW-UP

A participant will be considered lost to follow-up if he or she fails to return for the 2 scheduled follow up Otolaryngology clinic visits and is unable to be contacted by the study site staff.

The following actions must be taken if a participant fails to return to the clinic for a required study visit:

- The site will attempt to contact the participant and reschedule the missed visit within 2 weeks and counsel the participant on the importance of maintaining the assigned visit schedule.
- Before a participant is deemed lost to follow-up, the investigator or designee will make every
 effort to regain contact with the participant (where possible, 3 telephone calls and, if necessary,
 a certified letter to the participant's last known mailing address or local equivalent methods).
 These contact attempts should be documented in the participant's medical record or study file.
- Should the participant continue to be unreachable, he or she will be considered to have withdrawn from the study with a primary reason of lost to follow-up.

In an effort to minimize failure to follow up, we will incentivize subject with a \$50 payment, to be provided at the follow up visits.

STUDY ASSESSMENTS AND PROCEDURES

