1.30 POPULATIONS FOR ANALYSES

• Intention-to-Treat (ITT) Analysis Dataset (i.e., all randomized participants):

Placebo group (n=30) NAC treated group (n=30)

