1.31 STATISTICAL ANALYSES

General Approach

1.31.1

Data (SIT scores, QOD scores) will be presented as means with standard deviations, as well as range. Placebo and NAC-treated groups will be compared statistically, with p<0.05 considered significant, via two-tailed t-test. If data are not normally distributed, nonparametric testing or appropriate post-hoc corrections will be applied.

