1.31.2 ANALYSIS OF THE PRIMARY EFFICACY ENDPOINT(S)

Primary endpoint is SIT score at 1 month and 3 months.

Placebo and NAC-treated groups will be compared. SIT (mean ± sd) will be compared via two-tailed t-test.

SIT scores may range from 0-40, and normal scores are well-established. An assignment of normosmia, mild hyposmia, moderate hyposmia, severe hyposmia, anosmia, or probable malingering can be made based on SIT score.

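### Missing SIT scores are handled as a matter of numbers only; a repeated-measures model of both visits would use the 1-month score that the 3-month t-test leaves out

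*Combined protocol and SAP*

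**What the plan says.** All references are to the combined protocol and SAP.

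- **Section 1.29** discusses dropout, withdrawal and missing data as an influence on power and answers with numbers: "to compensate for such issues, we have increased our sample size by 5 subjects per group". It states no expected loss rate.
- **Section 1.31.2** makes SIT at 1 and 3 months the primary endpoint and says "SIT (mean ± sd) will be compared via two-tailed t-test". Section 1.31.3 does the same for QOD. The statistical sections contain no repeated-measures model, imputation rule, missing-data assumption or sensitivity analysis.
- **Section 1.30** names one analysis set, "Intention-to-Treat (ITT) Analysis Dataset (i.e., all randomized participants", with 30 per arm. Section 1.22 removes patients who do not finish the course from the outcome analysis and provides for replacing those who withdraw.
- **Sections 1.15, 1.23 and 1.26.8** describe payment, re-contact after a missed visit, and a mailed SIT and QOD for either follow-up visit.
- **Sections 1.11 and 1.24** use the 12-item brief test at screening; the 40-item SIT is used only at the two follow-up visits.

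**The concern.** Adding patients restores precision, but it does not make those tested at 3 months comparable between arms. A two-sample t-test at 3 months is an available-case analysis: anyone without that score drops out of that comparison. Their 1-month SIT, if they have one, still counts in the 1-month test but contributes nothing at 3 months, although it is probably the best predictor of the missing value. The screening test cannot stand in for it, being on a different scale.

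Whether a patient completes a later smell test could plausibly depend on whether smell has returned. If so, the 3-month difference may be attenuated or, if the dependence differs by arm, shifted even when the drug does nothing. The named set of all randomized participants also cannot be analysed by these t-tests once any SIT is missing, and the plan does not say what to do then.

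**Working it through.** **1. The plan's own figure.** Inputs from sections 1.29 and 1.31: "Type I error rate (alpha): 0.05", two-sided ("with p<0.05 considered significant, via two-tailed t-test"); "Power level: 0.8"; "Placebo group, mu1: SIT=17 ± 10"; NAC mean 25, SD 10. The difference is 25 − 17 = 8.

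n per arm = 2 × [10 × (1.960 + 0.842) / 8]² = 24.53, rounded up to 25. Adding 5 gives 30, as stated. (The exact t calculation needs 26, a trivial difference.)

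**2. What the allowance covers.** 5/30 = 16.7%, and 25 / (1 − 1/6) = 30. At 25 evaluable per arm, 8 / (10 × √(2/25)) = 2.828 and 2.828 − 1.960 = 0.868, so power is 0.807 (exact t 0.791). At 30% loss, 21 per arm remain and power is 0.736 (exact t 0.716). These figures assume loss unrelated to outcome.

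**3. What happens if loss is related to outcome.** The documents give neither a between-visit correlation nor a loss mechanism, so these are assumptions. Simulated trials had 30 per arm, bivariate normal SIT with SD 10, the same true difference at both visits, correlation 0.7, and 16.7% of 3-month scores missing. Where loss depends on a score, the logit slope is 0.10 per SIT point. The available-case t-test is compared with a likelihood analysis of both visits. Ranges span repeated runs.

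| Loss at 3 months | True difference | t-test | Likelihood, both visits |
|---|---|---|---|
| Unrelated to score | 8 | power 79% | power 81–83% |
| Depends on 1-month SIT, same rule in both arms | 8 | estimate about 7.4, power 74–76% | estimate 7.9–8.0, power 80–82% |
| Same rule in both arms | 0 | no bias, error about 5% | no bias, error about 5% |
| Depends on 1-month SIT in one arm only | 0 | error 6–7% | error about 5% |
| Opposite rules in the two arms | 0 | error 11% | error about 5% |
| Depends on the unseen 3-month SIT, same rule | 8 | estimate 7.2–7.3 | estimate about 7.6 |

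At 30% missing, the same-rule t-test gives 7.1–7.4 with about 65% power over correlations 0.5–0.8, against 72–81% power for the likelihood analysis. The opposite-rules error is then 21–22%.

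**4. Limits of the check.** The likelihood analysis was a factored likelihood for two visits, not the REML fit proposed below. The simulation ignores the 0–40 bounds of the SIT.

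**The case against.** **Other measures exist.** A reader might infer that 5 extra patients per arm are the trial's sole answer to missing data. They are not: sections 1.15, 1.22, 1.23 and 1.26.8 add payment, replacement, rescheduling, calls and mailed tests. Mailing also weakens the idea that a patient must come back to a smell clinic. With full replacement to 30 evaluable per arm, exact t power would be 0.861. This stands as far as numbers go. It does not say how the remaining gaps are analysed, and replacing patients does not recover the missing outcomes.

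**The 1-month score is not thrown away.** It enters the 1-month comparison, itself a primary time point. It is left out only of the 3-month one. That separate tests are meant is the natural reading of section 1.31.2, not its literal wording.

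**Section 1.23.** A reader might infer from "fails to return for the 2 scheduled follow up Otolaryngology clinic visits" that someone missing only the later test is never counted as lost. The text does not establish this: the next sentences apply to any required visit missed and end in withdrawal if the participant stays unreachable. The wording is at most ambiguous, and nothing here rests on it.

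**Inflated error is not a property of the plan.** In a double-blind trial, opposite dropout patterns with no drug effect are an extreme case. With one common rule there is no null bias. With unrelated loss, the t-test's 0.791 against 0.80 reflects the normal-approximation formula, not missing data.

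**The model is not a cure.** If return depends on current, unseen smell, roughly half the bias remains. This stands, and is why a sensitivity analysis is part of the fix.

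**Conclusion.** The point holds in a conditional form. The analysis plan allows for missing SITs only through sample size, and the 3-month comparison as planned ignores information already collected. The benefit of changing is modest if loss is unrelated to recovery (about 2–4 power points). It is moderate if loss follows the 1-month score by one rule in both arms: about 0.6 SIT points of attenuation (8 − 7.4) and some 6 power points. It matters for type I error only if the mechanism differs by arm. All these sizes rest on the assumed correlation of 0.7, 16.7% missing and slope of 0.10 per point; the documents can neither confirm nor exclude them. The documents do not support saying that the planned test is biased as it stands, or that 30 per arm is too few. This is a worthwhile, cheap improvement to the analysis rather than a flaw that invalidates the design.

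**What to change.** 1. In section 1.31.2, replace the separate t-tests with one mixed model for repeated measures of SIT at both visits: arm, visit and arm-by-visit terms, unstructured covariance, REML, Kenward-Roger degrees of freedom. Include every randomized participant with at least one follow-up SIT, and report the arm difference at each visit.
2. Reconcile this set with section 1.22, which excludes incomplete-course patients, and section 1.30, which names all randomized participants. State how replaced patients are treated.
3. Add a delta-shift (tipping-point) sensitivity analysis for missing SITs. It should cover randomized participants with no follow-up SIT, whom the model cannot include.
4. Report missing SITs by visit and arm.
5. Use the same model for QOD in section 1.31.3.

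The cost is SAP wording and slightly more analysis work. The model relies on data being missing at random given arm and observed SIT scores, a weaker assumption than the available-case t-test makes. No new data are needed, and N stays at 30 per arm.

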1.30 POPULATIONS FOR ANALYSES

• Intention-to-Treat (ITT) Analysis Dataset (i.e., all randomized participants):

Placebo group (n=30) NAC treated group (n=30)

1.31 STATISTICAL ANALYSES

General Approach

1.31.1

Data (SIT scores, QOD scores) will be presented as means with standard deviations, as well as range. Placebo and NAC-treated groups will be compared statistically, with p<0.05 considered significant, via two-tailed t-test. If data are not normally distributed, nonparametric testing or appropriate post-hoc corrections will be applied.

1.31.2 ANALYSIS OF THE PRIMARY EFFICACY ENDPOINT(S)

Primary endpoint is SIT score at 1 month and 3 months.

Placebo and NAC-treated groups will be compared. SIT (mean ± sd) will be compared via two-tailed t-test.

SIT scores may range from 0-40, and normal scores are well-established. An assignment of normosmia, mild hyposmia, moderate hyposmia, severe hyposmia, anosmia, or probable malingering can be made based on SIT score.

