1.3 SCHEDULE OF ACTIVITIES (SOA)

Procedur Informed conser		X	Day -2 to 0	Enrollment/Baseline	Day 0	Home treatment	Day 1-6	Study Visit 2	Day 30 +/-7 days	Study Visit 3	Month 4 +/- 3 weeks
Demographics		Х									
Medical history		Χ									
1.3.1.1.1.1	B-IT (Brief olfactio n test)	Х									
1.3.1.1.1.2	SIT (olfactio n test)In person or send by mail.							Х		Х	
1.3.1.1.1.3	QOD (questio nnaire)	Х						Х		Х	
1.3.1.1.1.4	Radiolo gic/Imag ing assessm ent	X									
Randomization		Х									
Physical exam, w	ith nasal	Χ									
endoscopy											
Vital signs		Χ		Χ				Χ		Χ	
1.3.1.1.1.5	Concom itant medicati on review	Х		X				Х		Х	
Pregnancy test		Χ									
1.3.1.1.1.6	Adminis ter study interven tion			Х		Х					
1.3.1.1.1.7	Adverse event review and evaluati on			X				X		Х	

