1.6.3 ASSESSMENT OF POTENTIAL RISKS AND BENEFITS

Existing evidence is consistent with a very positive risk to benefit assessment. Prior clinical trial with the exact NAC regimen in TBI patients reported no adverse effects. The treatment involves only a 1 week course of therapy. There are no existing alternatives. Basic science studies provide a wealth of evidence for promoting neuronal recovery using this drug.

OBJECTIVES AND ENDPOINTS

OBJECTIVES		ENDPOINTS		JUSTIFICATION FOR ENDPOINTS		
Primary						
To determine if early treatment with NAC after head injury results in improved olfactory function, compared to placebo.		1.6.3.1.1.1.1	Olfactory function at 1 and 3 months post- enrollment, as measured by Smell Identification Test (SIT).	1.6.3.1.1.1.2	sIT is a validated test for olfaction. Time points of 1 and 3 months were chosen to test for early recovery of olfactory neurons versus evidence for successful regeneration, respectively.	
Secondary						
1.6.3.1.1.1.3	To assess olfactory- specific quality of life measure in treated versus placebo groups.	1.6.3.1.1.1.4	Questionnaire on olfactory dysfunction (QOD) scores at 1 and 3 months.	1.6.3.1.1.1.5	QOD is a validated tool for measuring quality of life related to olfactory loss.	

OBJECTIVES	ENDPOINTS	JUSTIFICATION FOR ENDPOINTS
Tertiary/Exploratory		
N/A		

STUDY DESIGN

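### SIT at 1 month and SIT at 3 months are both primary, each tested at two-tailed p<0.05, with no rule for success, so the stated alpha of 0.05 is not guaranteed

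*Combined protocol and SAP*

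**What the plan says.** Both visits are primary wherever the endpoint is stated: the synopsis (1.1), the Objectives and Endpoints table, 1.24, 1.28 and 1.31.2.

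- Section 1.31.2: "Primary endpoint is SIT score at 1 month and 3 months", compared between arms by two-tailed t-test.
- Section 1.31.1 sets the threshold: "with p<0.05 considered significant, via two-tailed t-test". The only corrections it mentions depend on non-normal data, not on multiple tests.
- Section 1.28 has a single SIT null hypothesis, with "Time period: 1 and 3 months post-enrollment".
- The Objectives and Endpoints table gives each visit its own purpose: "Time points of 1 and 3 months were chosen to test for early recovery of olfactory neurons versus evidence for successful regeneration".
- Section 1.29 plans one t-test with "Type I error rate (alpha): 0.05" and power 0.8. It assumes means of 17 and 25 with ± 10 in each arm, and does not say which visit this refers to.

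No section orders the two tests, divides alpha, defines a joint or repeated-measures test, or says what result makes the trial positive.

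**The concern.** The plan has one hypothesis, one alpha and one sample size calculation, but two primary tests. A trial that is significant at only one visit could be reported as a success or as a failure, and nothing written in advance decides which. If such a split counts as a win, the trial has two chances of a false positive at 0.05. If it does not, the stated power belongs to a different rule from the one applied. A rule chosen after unblinding would not be credible. Section 1.32.2 also lists the primary endpoint having been met as a possible reason to end the study, although no section defines when it is met.

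**Working it through.** **Inputs.** Section 1.29 gives a difference of 25 − 17 = 8, SD 10 (reading ± 10 as a standard deviation), alpha 0.05, power 0.8 and 30 per arm. It also says "we have increased our sample size by 5 subjects per group" to cover dropout and missing data. Section 1.31.1 makes the test two-tailed. The correlation r between the 1-month and 3-month test statistics is not in the documents; 0.5 to 0.9 is assumed.

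**The plan's own figure.** For one two-sided test, n per arm = 2(1.960 + 0.842)² × (10/8)² = 24.5, so 25, and 25 + 5 = 30. The stated size reproduces for a single two-sided test. The figure of 25 evaluable is derived in this way and is not stated. Section 1.22 replaces participants who withdraw, so 30 evaluable is also possible, and both sizes are shown. By the noncentral t distribution, single-test power is 0.791 at 25 per arm and 0.861 at 30.

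**Reading A: either visit is enough.** Under no effect, with Z1 and Z2 bivariate normal with correlation r:

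- two-sided familywise error = 1 − P(|Z1| < 1.96, |Z2| < 1.96)
- false claim of improvement = 1 − P(Z1 < 1.96, Z2 < 1.96)

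| r | Familywise error | False improvement |
|---|---|---|
| 0 (independent) | 0.0975 | 0.0494 |
| 0.5 | 0.0907 | 0.0454 |
| 0.7 | 0.0835 | 0.0417 |
| 0.8 | 0.0781 | 0.0390 |
| 0.9 | 0.0704 | 0.0352 |

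The benchmarks for one test are 0.05 and 0.025. Simulated pairs of t-tests agree with the familywise column.

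**Reading B: both visits must be significant.** The error rate does not exceed 0.05. Power was simulated with two correlated pooled t-tests, an 8-point effect at both visits and complete data at both:

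| r | 25 per arm | 30 per arm |
|---|---|---|
| 0.5 | 0.674 | 0.774 |
| 0.7 | 0.704 | 0.793 |
| 0.8 | 0.719 | 0.804 |
| 0.9 | 0.738 | 0.822 |

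**How often the visits disagree.** In the same simulations, exactly one visit is significant in 23.4% (r = 0.5) to 10.5% (r = 0.9) of trials at 25 per arm, and in 17.5% to 8.0% at 30. As a check, this should equal 2 × (single-test power − both-visit power). At 25 per arm and r = 0.5 that is 2 × (0.791 − 0.674) = 0.234.

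**The case against.** The strongest objection is about weight. This is a single-site Phase 2 trial of 60 participants with a directional alternative, so a false finding of harm would not support its claim. Counting only false claims of improvement, the error stays below 5% even under Reading A with independent tests. Results for both groups are to be presented and individual data tabulated, so a split result would be visible. All of this is true. But the plan chose two-tailed testing at 0.05, which allows 2.5% in the direction of benefit, and it declares a superiority hypothesis with a stated alpha and power. Showing both results does not settle whether a split is a success.

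A second objection is that the text may intend both visits to be required, since section 1.31.2 speaks of one endpoint and section 1.28 puts both times under one null hypothesis. That reading is open. The separate purposes in the objectives table point the other way, and the documents do not choose. Under the both-visits reading alpha is safe, but the power was never calculated.

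Third, the objectives table expects different biology at each visit, so an equal 8-point effect at both is not necessarily the sponsor's expectation. This stands: the both-visit power and split rates are illustrations under stated assumptions, not forecasts.

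**Conclusion.** The concern holds. The plan secures its stated alpha only if both visits must be significant, and it has calculated its stated power only for a single test. With correlation 0.5 to 0.9, counting either visit gives a familywise error of 7.0% to 9.1% and a false-improvement rate of 3.5% to 4.5%. Requiring both leaves power below 0.8 throughout that range at 25 evaluable per arm, and below 0.8 at correlations of 0.5 and 0.7 with 30. The sizes depend on the assumed correlation. The absence of a success rule does not, and it affects the trial's main conclusion, so it should be settled before unblinding.

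**What to change.** State the success rule before unblinding, in the same terms in the synopsis, the objectives table and sections 1.28, 1.29 and 1.31.2.

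**Preferred.** The sponsor names one visit as the single primary, tested two-sided at 0.05. SIT at the other visit is tested two-sided at 0.05 only if the first test is significant; otherwise it is supportive. Alpha stays at 0.05, and the 25 + 5 calculation stands for the first test.

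The choice of visit is the sponsor's, but two places should be reconciled with it. Section 1.29 supports the 8-point effect partly by reference to "a jump of more than a few points on a repeat SIT test after one" month, a retest interval that does not by itself tie the calculation to Visit 2. The Schedule of Activities places Visit 3 at "Month 4 +/- 3 weeks", while the endpoint is at 3 months.

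**If the visits stay on an equal footing,** use the Hochberg procedure: both are significant if both p-values are at most 0.05; otherwise only a visit with p at most 0.025 is. Its simulated two-sided familywise error is about 0.048 at r = 0.5 and 0.042 at r = 0.9. Restate per-visit power: about 0.76 at 25 per arm and 0.84 at 30 with an 8-point effect at both visits, or 0.70 and 0.79 (0.696 and 0.785) if only the 0.025 level is relied on.

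**If both visits must be significant,** say so and report the power under Reading B.

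**Cost.** The preferred change takes one or two sentences, with no added participants or visits and no loss of power for the first test. Its downside is that an isolated result at the second visit can only be supportive.

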1.11 INCLUSION CRITERIA

In order to be eligible to participate in this study, an individual must meet all of the following criteria:

- Admitted to Ryder Trauma Center for observation acutely following head injury (i.e. concussion), with documented hyposmia or anosmia by University of Pennsylvania Brief Smell Identification Test (SIT). (The Brief smell identification test B-SIT is a rapid and effective 5 minute screening test. This 12 item version of the Smell Identification Test is useful for detecting smell loss in situations where less than five minutes of time are available)
- 2. Male or female, aged 18 years or older
- 3. Provision of signed and dated informed consent form
- 4. Stated willingness to comply with all study procedures and availability for the duration of the study
- 5. Ability to take oral medication and be willing to adhere to the NAC regimen
- 6. For females of reproductive potential: use of highly effective contraception for at least 1 month prior to screening and agreement to use such a method during study participation and for an additional 4 weeks after the end of NAC administration

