1.22 PARTICIPANT DISCONTINUATION/WITHDRAWAL FROM THE STUDY

Participants are free to withdraw from participation in the study at any time upon request.

An investigator may discontinue or withdraw a participant from the study for the following reasons:

- Pregnancy
- Significant study intervention non-compliance
- If any clinical adverse event (AE), laboratory abnormality, or other medical condition or situation occurs such that continued participation in the study would not be in the best interest of the participant
- If the participant meets an exclusion criterion (either newly developed or not previously recognized) that precludes further study participation

The reason for participant discontinuation or withdrawal from the study will be recorded on the NAC Case Report Form (CRF). Subjects who sign the informed consent form and are randomized but do not receive the study intervention may be replaced. Subjects who sign the informed consent form, and are randomized and receive the study intervention, and subsequently withdraw, or are withdrawn or discontinued from the study, will be replaced. Patients who do not complete the full course of study drug/placebo will be noted in the results tables, and they will not be included in the statistical analysis of outcome measures, since this is a simple comparison of SIT score between patients receiving a 1 week course of NAC versus placebo.

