1.24 EFFICACY ASSESSMENTS

The primary outcome measure is olfactory ability at 1 and 3 months, measured via the SIT, in head trauma patients. Patients will be identified from the population admitted for observation at Ryder trauma following TBI. Co-investigators on this protocol oversee the trauma unit, round on the admitted patients on a daily basis, and will therefore identify candidates as those patients sustaining a TBI from blunt head injury requiring overnight observation. Relevant standard of care data from the chart will be collected in a HIPPA-compliant fashion, to specifically include (1) history describing mechanism of injury, (2) results of head CT and (3) physical exam upon presentation, with Glascow Coma Score or other standard head trauma assessment details. No additional imaging is required for the study or efficacy measure; however imaging obtained as part of standard routine care available in the medical record will be reviewed. Those patients with severe poly-trauma and/or ongoing intubation or inability to participate in the SIT test will be excluded. The candidate patients will be administered the Brief SIT to assess olfaction. Those with abnormal scores will be offered enrollment in the study. There are only 3 procedures involved in the study to assess efficacy: (1) SIT measures (2) Administration of study medication or placebo, (3) the QOD quality of life questionnaire.

- The SIT is a self-administered 40-item test involving microencapsulated (scratch-and-sniff) odors with a forced-choice design. There are 4 booklets with 10 questions each, asking the subject to identify which of 4 answers best described the odor. Total scores are categorized, based on normative data, as normal, mild hyposmia, moderate hyposmia, severe hposmia, total anosmia, or probable malingering. The test was developed at University of Pennsylvania as part of an NIH-funded program project and is widely used as a standard assessment of olfactory function. We will use the Brief Smell Identification Test that is a rapid and effective 5 minute test during the Screening Visit. This item version of the Smell Identification Test is useful for detecting smell loss in situations where less than five minutes of time is available. For the follow up Visit 2 and Visit 3, we will use the full SIT.
- The QOD is a validated olfactory-specific quality of life questionnaire and is attached.

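### SIT and QOD are compared by unadjusted t-tests although baseline B-SIT and QOD are collected: the tests are valid, but available precision goes unused

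*Combined protocol and SAP*

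**What the plan says.** Section 1.31.2 states for the primary endpoint, at 1 and 3 months, that "SIT (mean ± sd) will be compared via two-tailed t-test". Section 1.31.3 gives the same test for QOD. Section 1.31.1 allows one departure: "If data are not normally distributed, nonparametric testing or appropriate post-hoc corrections will be applied". No covariate, change score or model is named.

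Both baselines exist. Section 1.11 admits only patients "with documented hyposmia or anosmia by University of Pennsylvania Brief Smell Identification Test (SIT"), so every enrolled patient has a B-SIT score. The schedule in section 1.3 marks the QOD at screening as well as at Visits 2 and 3. Section 1.31.5 uses the enrolment smell score only to describe the arms.

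The smell test changes after baseline. Screening uses the 12-item version, and section 1.24 says: "For the follow up Visit 2 and Visit 3, we will use the full SIT", which has 40 items.

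Section 1.29 sizes the trial on a t-test with means of 17 and 25, SD 10, alpha 0.05 and power 0.8. It adds 5 patients per arm for dropout.

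**The concern.** The plan expects patients of varied severity. Section 1.29 assumes an SD of 10 and cites a review in which "a range of SIT scores are reported in the 7-27 score range, for mild-moderate TBI". If severity at entry predicts the later score, that predictable part of the variance stays in the t-test's standard error, where a covariate would remove it. A SIT change score cannot be formed because the two tests have different scales, so covariate adjustment is the direct way to use the baseline.

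At stake is precision: a wider confidence interval and somewhat lower power in a trial of 60 patients. Bias and type I error are not in question. A chance imbalance at baseline can shift the raw difference, but the t-test's standard error already allows for that.

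**Working it through.** **Inputs.** From section 1.29: difference 25 − 17 = 8, SD 10, alpha 0.05, power 0.8, 25 per arm plus 5. Two-sided testing comes from section 1.31.1. The within-arm correlation r between baseline and follow-up is not in the documents. It is assumed and shown over a range.

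**The plan's own figure.** By normal approximation, n per arm = 2 × 10² × (1.960 + 0.842)² / 8² = 24.5, so 25. Adding 5 gives 30 per arm and 60 in total, which matches section 1.29. The exact two-sided t-test needs 25.5, so 26. Exact power is 0.791 at 25 per arm and 0.861 at 30.

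**Formulas, n per arm.**
- t-test: SE = 10 × √(2/n), with 2n − 2 degrees of freedom.
- ANCOVA: SE = 10 × √(1 − r²) × √(2/n) × √(1 + 1/(2n − 4)), with 2n − 3 degrees of freedom. The last factor charges for estimating the slope.
- Power is from the two-sided noncentral t with noncentrality 8/SE. The 95% CI half-width is the 97.5% t quantile × SE.

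**Example, n = 25.** For the t-test, SE = 10 × √(2/25) = 2.83 and the half-width is 2.011 × 2.83 = 5.69. For ANCOVA at r = 0.3, SE = 10 × 0.954 × 0.283 × 1.011 = 2.73 and the half-width is 2.012 × 2.73 = 5.49.

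| Analysis | Power, 25 per arm | CI half-width, 25 per arm | Power, 30 per arm |
|---|---|---|---|
| t-test | 0.791 | 5.69 | 0.861 |
| ANCOVA, r = 0 | 0.782 | 5.75 | 0.855 |
| ANCOVA, r = 0.2 | 0.799 | 5.64 | 0.869 |
| ANCOVA, r = 0.3 | 0.819 | 5.49 | 0.886 |
| ANCOVA, r = 0.5 | 0.886 | 4.98 | 0.936 |

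Simulation of 40,000 trials per setting gave ANCOVA power of 0.798, 0.822 and 0.885 at 25 per arm, and 0.868, 0.886 and 0.936 at 30, for r = 0.2, 0.3 and 0.5.

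**Break-even.** ANCOVA and the t-test have equal power at r = 0.149 with 25 per arm and r = 0.135 with 30.

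**Equivalent sample size.** The adjusted analysis at 25 per arm has the power of an unadjusted one with 25.4, 26.8 or 32.3 per arm at r = 0.2, 0.3 or 0.5.

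**Chance imbalance.** A baseline difference of one standard error between arms of 30 moves the raw SIT difference by r × 10 × √(2/30) = r × 2.58. That is 0.5, 0.8 or 1.3 points at r = 0.2, 0.3 or 0.5.

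**QOD.** Section 1.29 says "We have no specific guides for mean or variance", so no power figure can be computed. In large samples, adjustment multiplies the variance of the treatment difference by 1 − r².

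**The case against.** The strongest case against is that nothing is broken. The planned test is valid and the sample size reproduces. The gain rests on an r that the documents do not supply, and there are reasons to expect it to be low: the baseline is a 12-item test taken within days of injury, and entry is restricted to abnormal scores. The 7 to 27 range comes from full SIT scores in a cited review. It shows neither the spread of B-SIT among eligible patients nor its prognostic value. At r = 0.2 the gain is under one percentage point of power, or 0.4 of a patient per arm, and below about 0.15 there is a small loss. The 79% figure also takes the whole dropout allowance as spent, whereas section 1.22 says that treated patients who "and subsequently withdraw, or are withdrawn or discontinued from the study, will be replaced". At 30 per arm, power is already 0.86.

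All of this stands as a limit on the size of the benefit. It does not remove the point, because the costs are uneven: at most about 1 point of power is lost if baseline proves uninformative, against about 3 to 9 points gained at 25 per arm if r is 0.3 to 0.5, from data already being collected.

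For QOD the objection is stronger. The prognostic value of a score taken within days of injury is unknown, and the argument rests on the low cost alone.

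**Conclusion.** The concern holds as a missed improvement that should be made, not as a defect of validity. The SIT and QOD comparisons ignore baselines that the plan already collects. For SIT, with a difference of 8 and SD 10, adjustment is worth about 1 to 3 percentage points of power at r of 0.2 to 0.3, at either 25 or 30 per arm. At r = 0.5 it is worth about 9 points at 25 per arm and 7 to 8 at 30. At r = 0 it costs less than 1 point. These figures rest on the assumed r, whose lower values are more likely, and on the plan's own means and SD. The benefit for QOD cannot be quantified. No change in sample size is needed.

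**What to change.** Before unblinding, amend sections 1.31.1 to 1.31.3 to name one main model per endpoint at each visit: ANCOVA of SIT on treatment and baseline B-SIT (0–12), and ANCOVA of QOD on treatment and baseline QOD. Report the adjusted mean difference with its 95% confidence interval. Keep the two-tailed t-test and the nonparametric test as sensitivity analyses, and say that the ANCOVA governs the conclusion. State how a missing baseline QOD will be handled. B-SIT should not be missing, because entry depends on it.

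Two conforming edits follow. In section 1.31.5, label the enrolment score as B-SIT on its 12-item scale, so that it is not read against the 0–40 outcome. In section 1.29, note that the sizing uses the unadjusted test.

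The cost is wording and one degree of freedom per model, with no added visit, test or patient. If r is below about 0.15, up to 1 percentage point of power is lost.
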